11 INVESTIGATOR RESPONSIBILITES AND GOOD CLINICAL PRACTICES

In conducting this medical device clinical investigation the Investigator is responsible for:

- Ensuring that a clinical investigation is conducted according to the Declaration of Helsinki, applicable local regulations, the signed Clinical Trial Agreement, and the Clinical Investigation Plan.
- Protecting the rights, safety, and welfare of Subjects under the Investigator's care; and
- Ensuring the integrity of the data.

Prior to the initiation of this clinical investigation at each site, the responsible Principal Investigator will acknowledge their understanding of this Clinical Investigation Plan (CIP) by signing the signature page. This signature confirms that the clinical investigation will be performed in compliance with the CIP.

11.1 Qualification of Principal Investigator and Investigational Site

The PI shall:

- be qualified by education, training and experience to assume responsibility for the proper conduct of the clinical investigation in accordance with ISO14155. Evidence of such qualifications of the PI and key members of the investigative site team shall be provided to the Sponsor through up-to-date CVs or other relevant documentation.
- be experienced in the field of orthopaedics and total knee replacement and trained in the use of the investigational device under consideration.
- disclose potential conflicts of interest, including financial, that interfere with the conduct of the clinical investigation and/or interpretation of results.
- be knowledgeable with the method of obtaining informed consent.

The PI shall be able to demonstrate that the proposed investigational site:

- has the required number of eligible subjects needed within the agreed recruitment period.
- has one or more qualified investigators, a qualified investigational site team and adequate facilities for the foreseen duration of the clinical investigation.

11.2 Institutional Review Board (IRB)/Ethics Committee (EC) Approval

All Principal Investigators must submit to their institution's IRB/EC for initial review a copy of the clinical investigational plan (CIP), a sample Informed Consent Document (ICD) provided by the Sponsor. Many institutions request modification of the ICD to satisfy specific institutional requirements. The use of a modified or unique Informed Consent Document is permitted provided that the document is reviewed and approved by the Sponsor. Additionally, all translated consent forms require IRB/EC approval.

All Principal Investigators must submit the Clinical Investigation for continuing review and any other additional required submissions to their IRB/EC according to their IRB/EC's policies and procedures.

Initial approval/favorable opinion and all continuing review approvals must be documented; originals of correspondence and approvals are to be filed by the Investigator and copies forwarded to the Sponsor.

11.3 Informed Consent

The Principal Investigator is responsible for maintaining source documents evidencing informed consent was obtained from study Subjects prior to participation in the study and the process followed to obtain consent.

If an Investigator performs any study-specific procedures and/or data collection without obtaining informed consent, the Investigator will report such action(s) to the Sponsor and the reviewing IRB/EC.

For further details and a description of the Informed Consent process, please refer to Section 8.1.2, Subject Informed Consent.

11.4 Protected Health Information

The Principal Investigator is responsible to inform study Subjects their personal data will be collected, processed, and confidentially maintained in accordance with local data privacy regulation and law.

United States: The Principal Investigator is responsible for taking the necessary steps to collect, process and maintain confidentiality of the Subject's personal data in accordance with data protection legislation including the Health Insurance Portability and Accountability Act of 1996 (HIPAA). Subjects will be asked to sign an Authorization for Release of Protected Health Information (PHI) for the purpose of this investigation. The authorization may be combined with the ICD, depending on local IRB preference.

Results from the Clinical Investigation may be published. However, Subject confidentiality will be maintained at all times and it will not be possible to identify individual Subjects from any data presented.

11.5 Subject Completion/Discontinuation from the Clinical Investigation

Any Subject is entitled to discontinue/withdraw from this clinical investigation for any reason without obligation and/or prejudice to further treatment. In addition, the Investigator may decide, for reasons of medical prudence, to withdraw a Subject.

The Investigator will clearly document the date and reason(s) for the Subject's discontinuation from this clinical investigation in the Subject Completion/Discontinuation eCRF and submit to DePuy Synthes Products Inc.

Please refer to Section 8.4 Discontinuation of Subject Participation for further details.

11.6 Source Documentation

The Investigator will maintain a complete, current and accurate case history (Source Documentation records) on each study Subject according to the usual procedure at the investigational site. Case histories, medical records, including progress notes, hospital charts, nurses' notes etc. Additional documents to be retained include:

- Signed original Informed Consent Document
- Completed Source worksheets (if used)
- Results of relevant diagnostic and laboratory tests

DSJ_2019_05, Rev D (FINAL) 24 August 2022 DePuy Synthes Products, Inc. - Confidential

- Intraoperative and post-operative complications and treatment, and
- Any other relevant information or documentation pertaining to the condition of the Subject.

Monitors may verify data reported in the electronic data capture (EDC) system against Subject source documents. The Investigator agrees that the Sponsor's employees or designees will have the right to audit and review pertinent medical records relating to this clinical investigation and the Subject will grant approval for such access to their medical records via the Informed Consent process.

11.7 Case Report Form Completion and Data Submission

Data will be captured within an electronic data capture system provided by DePuy Synthes Products Inc.

Electronic Case Report Forms (eCRFs) will be used to collect and submit all Subject data once a Subject is enrolled in the study. Investigative study sites are asked to transfer Subject data from the source PROMs into the eCRFs preferably within 2 weeks from the time the Subject was seen for their scheduled study visit.

Role-specific training on eCRF completion is required to be completed by the Investigator(s) and study support staff prior to initiating Subject enrolment.

The personal data recorded on all documents, including copy documents, and within the EDC system, will be regarded as confidential. The Investigator will be responsible for the timing, completeness and accuracy of the details entered within the electronic data capture system. All data entered in the database must have source documents in the Subject's medical records or source worksheets.

The respective eCRFs must be fully completed for each Subject. The Investigator's electronic signature will be obtained within the EDC system once all study data has been entered, cleaned and coded (and at interim analysis if applicable). Sign off can occur on a per form or per casebook level. Any changes to the data will break the Investigator's signature and sign off will need to be obtained again on the relevant data.

The patient-reported outcome measures (AKS, KOOS, EQ5D-5L, and FJS-12) will be recorded on paper-based or other validated electronic questionnaires. The data will then be transferred into the respective eCRF within the electronic data capture system by the Investigator or designee. The patient-reported outcomes measures captured on paper-based questionnaires must be stored in the Subject's binder as these will be considered to be the source document. Any errors on paper forms should be crossed out with a single stroke, initialed and dated. Typing correction fluid must not be used. The Investigator will retain one copy of each completed paper CRF in the medical notes.

The Investigator must record the Subject's participation in this clinical investigation in the Subject's medical notes. In addition, the Investigator must keep a separate list of all Subjects entered into this clinical investigation showing each Subject's name, date of birth and assigned Subject number (for identification purposes). A Patient Information log will be provided in the Investigator Site File for this purpose and remain at the site.

The Investigator should retain copies of all documents pertaining to this clinical investigation (including source documentation, the informed consent document and any other documents to identify the

Subjects) per the applicable retention period in your region⁴ or per your IRB/EC/RA after this clinical investigation is completed. In addition, if the Investigator moves/retires, etc., he should provide the Sponsor with the name and address of the person who will be responsible for the Subjects' clinical investigation related records.

Data queries will be generated by the system at the time of data entry, if applicable. Resolution of the queries will be the responsibility of the Investigator and investigation team members. Following completion of all data queries on each eCRF, the Investigator will be responsible for reviewing and confirming agreement to the data within the system.

The platform software has been validated in accordance with 21 CFR Part 11, European Commission's Directive on Data Protection and EU General Data Protection Regulation. Prior to being released for data entry, validation of the study level components (i.e., data entry screens, associated edit checks and workflow) will be conducted in accordance with approved user acceptance testing procedures. Access to this system will be controlled so that only authorized users will have the ability to enter into the system. The system is considered a closed system according to 21 CFR Part 11 Electronic Records; Electronic Signatures.

11.8 Protocol Adherence

The Investigator(s) agrees to conduct the study in accordance with this protocol. An Investigator must not make any changes in a study without first receiving approval from the Sponsor and IRB/EC, except when necessary to eliminate apparent immediate hazards to a Subject.

With the exception of emergency situations, no deviations to this CIP will be permitted. In the event of an emergency situation, the Investigator must notify the Sponsor immediately. The Site will be responsible for completing a Protocol Deviation eCRF within the EDC system, which will serve as Sponsor notification. IRB/EC/RA notification will be the responsibility of the Investigator.

If serious or repeated protocol deviations are found at a Site, either through study monitoring, data review or audit (internal or external), the Sponsor is able to take one, or more of the following actions:

- Issue Site retraining.
- Issue Corrective and Preventative Actions.
- Temporary Site suspension (see Section 12.4).
- Site termination (see Section 12.4).

11.9 CIP Amendments

If it becomes necessary to amend the Clinical Investigation, the nature of the amendment will be agreed between the Sponsor and the Principal Investigator(s) and this will be recorded with a justification for the amendment. The appropriate IRBs/ECs will be informed of any amendments.

⁴ for at least 5 years in the UK and for at least 3 years in the United States
DSJ_2019_05, Rev D (FINAL)
DePuy Synthes Products, Inc. - Confidential
24 August 2022

11.10 Reports

In fulfillment of study related requirements, the Investigator is responsible for preparing and submitting complete, accurate, and timely reports as described below.

Table 11-1: Investigator Reporting Responsibilities

Report	Description	Action
Withdrawal of IRB/EC approval	The Investigator will promptly notify the Sponsor of a withdrawal of approval by the reviewing IRB/EC or of the Investigator's part in an investigation within 2 weeks.	Preferably within 2 weeks (or less if required by local regulations)
Progress Report	If required by your IRB/EC, the Investigator is responsible for submitting progress reports on the investigation to the reviewing IRB/EC.	As required per your IRB/EC
Reports of deviations from the investigational plan	The Investigator will notify the Sponsor of any deviation from the Investigational Plan as soon as able. The Investigator will notify the IRB/EC of any deviation from the Investigational Plan per the IRB/EC requirements.	Per IRB/EC requirements;
Other	The Investigator will, upon request of a reviewing IRB/EC or Sponsor, provide accurate, complete, and current information about any aspect of the investigation.	As requested

The Principal Investigator may delegate a qualified associate(s) to complete one or more of the above functions. However, the Principal Investigator retains the overall responsibility for Subject safety, proper conduct of the study including obtaining Subject Informed Consent, compliance with this study plan, and the collection of all required data.

11.11 Investigator Site File

Each Investigator and all personnel from the investigational site must maintain accurate, complete, and current information about all aspects of this Clinical Investigation. This includes documentation relating to the Investigator's participation, Subject information and correspondence: electronic, written, and verbal, relating to any aspect of the clinical investigation. The records are maintained in the Investigator Site File consisting of, but not limited to, correspondence with other participating Investigators, the reviewing IRB/EC, and the Sponsor.

Upon receipt of copies of changes or revision updates to the Clinical Investigation Plan (otherwise known as the Study Protocol) from the Sponsor, the Investigator will add the updated document and Revision Log to the Investigator Site File. The outdated version will be filed.

11.12 Investigator Study Termination

The Investigator may prematurely terminate the clinical investigation at any time. Should this be necessary, the procedures will be arranged on an individual clinical investigation basis after review and consultation by both parties. In terminating the clinical investigation, the Sponsor and the Investigator will assure that adequate consideration is given to the protection of the Subject's interests, all documentation is archived per Section 11.7 and the appropriate bodies such as the IRB/EC/RA are informed as appropriate.

12 SPONSOR OBLIGATIONS

12.1 IRB/EC Approval

The Sponsor requires this Clinical Investigation Plan to be submitted to the IRB/EC for initial review and approval before implementation at each site. Additionally, all protocol amendments must be submitted to the IRB/EC for review and approval before implementation.

Each site is required to submit a copy of the IRB/EC initial approval, and any subsequent renewals to the Sponsor for filing in the study's Trial Master File. The site is to maintain the original documentation of the initial approval and renewals in the site's Investigator Site File.

12.2 Investigator Training, Study Initiation

Prior to enrolling Subjects in this study, the Investigator(s) and/or appropriate Site personnel will be trained on this Clinical Investigation Plan to include:

- All general aspects of study administration,
- Content and manner of administration of the questionnaires,
- All procedures in the protocol, and
- The procedure for e-data acquisition and transmission.

The Sponsor will provide hands on training to supplement the professional education and experience of the surgeon regarding the implant and surgical instruments when deemed necessary by the Sponsor.

12.3 Study Monitoring

Monitoring activities will follow the Sponsor standard operating procedures (SOPs), Clinical Monitoring Plan, applicable regulations and good clinical practices (GCPs). Monitoring will include onsite monitoring visits unless prevented by a global pandemic (e.g. COVID-19) or other unforeseen crisis. Remote monitoring may be conducted if deemed appropriate by the Sponsor (e.g., global pandemic).

During the visit, the Sponsor and authorized Sponsor representatives shall be given access to all study records, including study Subject medical records to ensure proper monitoring of this clinical investigation. The monitor's duties are to verify that:

- a) compliance with the CIP, any subsequent amendment(s) and regulatory requirements is maintained; deviations shall be discussed with the Principal Investigator(s) or authorized designee, documented and reported to the Sponsor.
- b) only authorized individuals, as detailed on the Delegation Log, are participating in the Clinical Investigation.
- c) the study device is being used according to the CIP or IFU.
- d) investigational site resources and the investigation site team remain adequate throughout the duration of the Clinical Investigation.
- e) the Principal Investigator continues to have access to an adequate number of subjects and study devices.
- f) signed and dated informed consent forms have been obtained from each subject at the point of enrolment or before any Clinical Investigation-related procedures are undertaken.
- g) source documents and other Clinical Investigation records are accurate, complete, up to date, stored and maintained appropriately.
- h) CRFs and queries are complete, recorded in a timely manner, and consistent with source documents.
- i) appropriate corrections, additions or deletions are made to the CRFs, dated, explained if necessary and initialed by the Principal Investigator or by his/her authorized designee; the monitor shall not make corrections, additions or deletions to the CRFs.
- j) all device- and procedure-related AEs, SAEs and Device Deficiencies are reported to the Sponsor, and all SAEs and Device Deficiencies that could have led to a SADE are reported to the sponsor without unjustified delay.
- k) all SAEs and deviations are reported to the EC, if required.
- I) all other required reports, notifications, applications, submissions and correspondence are maintained in the investigator's files and are accurate, complete, timely, legible, dated and identify the Clinical Investigation.
- m) subject withdrawal has been documented; the monitor shall discuss this with the Principal Investigator or his/her authorized designee.

- n) subject non-compliance with the requirements stated in the informed consent has been documented; the monitor shall discuss this with the Principal Investigator or his/her authorized designee.
- o) the Principal Investigator and investigation site team are informed and knowledgeable of all relevant document updates concerning the clinical investigation.
- p) any corrective and preventive actions, as needed, have been implemented and are effective.

The Monitor, or representatives from the Sponsor, will be responsible for establishing the schedule and procedures to be followed for monitoring this clinical investigation and may also include the monitoring of the surgical procedure. The Clinical Investigator will receive reasonable notification prior to each monitoring visit during the course of this clinical investigation. At each visit, the Clinical Investigator will be expected to co-operate with the Monitor (and occasionally other Sponsor personnel) for the review and verification of all eCRFs and any additional records as may have been previously arranged between the Clinical Investigator and the Monitor. At each visit the Clinical Investigator will also be expected to co-operate with the Monitor for the review and verification of the device supply and device returns.

If under certain circumstances (i.e. limited access for sponsor study personnel to hospitals due to Covid-19 pandemic) on site monitoring is not possible, Sponsor may plan for remote monitoring and source data review or verification, where applicable. Details will be described in the study specific documents, such as monitoring plan, project operations manual etc.

12.4 Sponsor Study Termination

The Sponsor may prematurely terminate or suspend the clinical study as a whole or at an individual investigational site for significant and documented reasons. Reasons for premature termination or suspension include, but are not limited to safety, inadequate recruitment, Principal Investigator compliance, device-related problems, alignment with business strategy or administrative issues.

In the event of the study being terminated, any enrolled Subjects that have not yet had the surgical procedure would be treated as per their surgeon's standard practice using implants and instruments of the surgeon's choice. All enrolled Subjects would continue to be cared for by their surgeon according to his/her standard of care. No further study-related procedures or data collection would occur.

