8.3.4 Adverse Event Reporting Guidelines

8.3.4.1 AE Reporting by Site to Sponsor

Subjects should be encouraged to report AEs spontaneously or in response to general, non-directed questioning (e.g. "How has your health been since your last visit?"). The Subject may volunteer information relating to AEs at any time during the Study. If an event occurs at an outside institution, the Investigator should attempt to obtain, if possible, required AE information.

All SAEs and all Device and/or Procedure-Related AEs must be reported to the Sponsor, regardless of classification, severity or outcome. The Investigator is responsible for ensuring that all protocol reportable

DSJ_2019_05, Rev D (FINAL) 24 August 2022

AEs observed by the Investigator (or designee), or reported by the Subject, that occur from the intraoperative time frame through to the end of the Study (either study completion or withdrawal of consent) are properly assessed, recorded and reported. All protocol reportable AEs must be documented in the study Subject's medical records (source documents) and reported in the database on the Adverse Event eCRFs. All AEs will be monitored until they are adequately resolved or explained. When a Subject ends participation in the study (either through study completion or consent withdrawal) an AE must be designated either as "resolved" (end date must be provided), or as "ongoing."

Table 8-7: Adverse Event Reporting Requirements to Sponsor

Type of Adverse Event	Reporting Requirements
SAEs (including SADEs, USADEs and	Report to Sponsor by completing an AE eCRF or by direct
ASADEs)	contact to Sponsor (i.e. via phone or e-mail) immediately
All Implant Device Deficiencies	upon awareness of event but no later than 72 hours.
(including those that potentially could	
have led to an AE/SAE*)	If related to an Implant/Instrument Device Deficiency, also
	complete a Device Deficiency eCRF as soon as possible but
	no later than 72 hours.
AE (Device and Procedure Related,	Report to Sponsor by completing an AE eCRF or by direct
including ADEs and UADEs). See Table	contact to Sponsor (i.e. via phone or e-mail) immediately
8.5 for further definition of AE	upon awareness of event but no later than 72 hours.
relatedness	
AEs related to a Device Deficiency	Report to Sponsor immediately upon awareness of event
	but no later than 72hrs, in line with Device Deficiency
	reporting requirement above.
All other AEs not listed above	Report to Sponsor within 2 weeks of awareness.

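### Section 12.4 ends all study data collection on termination, even when the reason is safety or a device problem, and so conflicts with Section 8.3.4.1 on open adverse events

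*Combined protocol and SAP*

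**What the plan says.** Section 12.4 (Sponsor Study Termination) begins: "The Sponsor may prematurely terminate or suspend the clinical study as a whole or at an individual investigational site". The reasons it lists "include, but are not limited to safety, inadequate recruitment, Principal Investigator compliance, device-related problems", followed by business and administrative grounds. On termination, subjects not yet operated on are treated outside the study. For the rest, "All enrolled Subjects would continue to be cared for by their surgeon according to his/her standard of care", and "No further study-related procedures or data collection would occur". The rule does not vary with the reason. It makes no exception for knees already implanted and provides no closing contact. It is tied to termination; the section gives no data rule for suspension.

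Section 8.3.4.1 (AE Reporting by Site to Sponsor) says: "All AEs will be monitored until they are adequately resolved or explained". It runs AE reporting from surgery to the end of the study, which it glosses as study completion or withdrawal of consent. Sponsor termination is not mentioned. It adds: "When a Subject ends participation in the study (either through study completion or consent withdrawal) an AE must be designated either as" resolved, with an end date, or ongoing. Table 8-7 gives sites at most 72 hours from awareness to report serious events and device- or procedure-related events.

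Sections 6.2 and 6.3 plan Kaplan-Meier survivorship of the tibial base at 1, 2 and 5 years (secondary) and at 3 and 4 years (tertiary). Section 9.6 places the adverse event analyses and the Kaplan-Meier analysis of revisions on the Safety analysis set.

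**The concern.** The tibial base stays in the knee after the study stops. If the Sponsor stops because of a safety signal or a device problem, the knees already implanted are the ones whose further course bears on that signal. Section 12.4, followed as written, closes the study's record on them at that moment. A site holding an open device-related event on the termination date would have two instructions: Section 8.3.4.1 tells it to keep monitoring, and Section 12.4 tells it to collect nothing more.

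Two kinds of information are at stake. The first is the later course and outcome of events open at the stop. The second is revision status. Without a closing contact, a knee's status is known only up to the subject's last visit or report, so a revision between that point and the stop could be missed as well as any revision after it.

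**Working it through.** The plan states no figure on this point. The check is a comparison of text, followed by simple arithmetic on how much follow-up would exist at a stop.

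**1. The two rules side by side**

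| Question | Section 12.4 | Section 8.3.4.1 |
|---|---|---|
| What happens to an open AE at Sponsor termination? | Data collection ends | Monitoring continues until the event is resolved or explained |
| Does the reason matter? | No | Not addressed |
| Is Sponsor termination named? | Yes, as the trigger | No; only completion and consent withdrawal are named |
| Are AEs already known on record? | Not addressed | Yes, within 72 hours if serious or device- or procedure-related |

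**2. Does another section restore follow-up?** Section 8.8 leaves subjects withdrawn from the study in their surgeon's standard of care. Section 3.2 expects national joint registries to supply longer-term survivorship, but does not present them as a substitute after termination. Neither brings later events or revisions into the study database.

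**3. Follow-up in hand at a stop**

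Inputs: at least 600 implanted subjects (Section 7) and recruitment completed in 2.5 years for each configuration (Section 1, Study Duration). Assumptions: both configurations recruit over the same 2.5 years, accrual is uniform, and there is no attrition. The stop date is also an assumption.

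For a stop *t* years after the first implant, the number of knees past *y* years is 600 × min(2.5, max(0, *t* − *y*)) / 2.5.

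Stop at the end of accrual, *t* = 2.5:

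- past 1 year: 600 × 1.5/2.5 = 360
- past 2 years: 600 × 0.5/2.5 = 120
- past 3, 4 or 5 years: 0, because no knee has more than 2.5 years

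Moving the stop one year either way:

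| Stop (years) | Implanted | Past 1 year | Past 2 years | Past 3 years | Past 4 or 5 years |
|---|---|---|---|---|---|
| 1.5 | 600 × 1.5/2.5 = 360 | 600 × 0.5/2.5 = 120 | 0 | 0 | 0 |
| 2.5 | 600 | 360 | 120 | 0 | 0 |
| 3.5 | 600 | 600 | 360 | 120 | 0 |

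Attrition lowers these counts. Section 9.7 allows up to 15% at 1 year; applied to the 360, that leaves 360 × 0.85 = 306.

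**4. Consequence for the planned analysis.** With a stop at 2.5 years, the 3-, 4- and 5-year estimates cannot be produced. The 1- and 2-year estimates can be, on reduced numbers, but they omit any revision unreported on the termination date.

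**The case against.** The strongest reply is that the sections can be read together. The mention of completion and consent withdrawal in Section 8.3.4.1 cannot be exhaustive, because Sections 8.4, 8.5 and 8.7 also end participation through death, revision of the femoral or tibial component, the surgeon's decision and loss to follow-up. Section 8.3.4.1 itself accepts events left as ongoing when participation ends. Termination could be treated as one more such ending. The effect also arises only if the Sponsor terminates; nothing obliges it to terminate rather than suspend over a device problem. This narrows the point but does not remove it. The text does not say that termination is handled this way, and marking an event ongoing records neither its outcome nor a later revision.

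A reader might infer more than the documents support:

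- **That open adverse events would go unrecorded.** The 72-hour rule means that serious and related events known to the site should already be on record. Their later course is what would be lost.
- **That the harm behind a stop could not be measured.** Whatever prompted the stop was observed before it, and Kaplan-Meier methods accommodate censoring. Section 3.2 singles out the first year for initial fixation problems, and 360 knees would have passed that point in the central scenario. The later estimates are truncated.
- **That later revisions would be recorded nowhere.** They would be lost to the study, but surgeon care continues and registries may capture some.
- **That a number of missed revisions can be given.** The documents contain no revision rate for this base, so a count would rest on an outside rate, a chosen stop date and no attrition.
- **That the absence of a data monitoring or events committee leaves nobody to follow subjects.** Such bodies review data. The plan has a Safety Lead (Section 8.3.5) and ethics and regulatory oversight.
- **That Section 11.12 contains a protection missing here.** Its wording, "adequate consideration is given to the protection of the Subject's interests", is general and imposes no duty to collect data.

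**Conclusion.** The point holds in limited form. Section 12.4 states a rule that would reduce safety information if followed, makes no exception for termination on safety or device grounds, and conflicts with Section 8.3.4.1 on open events. The loss consists of the later course and outcome of open events, base revisions unreported at the stop or occurring after it, and the part of the Kaplan-Meier curve beyond termination.

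The size depends on when a stop occurs. The central case of 360 knees past 1 year, 120 past 2 years and none at 3 to 5 years rests on uniform accrual, a stop at 2.5 years and no attrition. The conflict between the sections rests on none of these assumptions. No planned analysis changes unless the Sponsor terminates. The data rule under suspension is unstated.

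**What to change.** Amend the last sentence of Section 12.4 and align Section 8.3.4.1 with it:

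1. On termination for any reason, serious events and device- or procedure-related events open at that date are followed until resolved or explained.
2. Each implanted, consenting subject still in follow-up has one close-out contact. It records adverse events and implant status: revision yes or no, component and date. The Exhibit F phone script and mailer already ask about new problems and surgery to the study knee and request details; prompts for component and date can be added.
3. These data enter the Safety analysis set and the Kaplan-Meier analysis. State that the Section 8.5 exclusion of data after withdrawal does not apply to them.
4. Name Sponsor termination in Section 8.3.4.1 and state which data continue to be collected during a suspension.

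The change concerns data collection only; care stays with the surgeon. It costs a short amendment and limited site contact work at close-out, which site agreements may need to cover. Longer contact after a safety- or device-driven termination would give more information on late revisions. It could commit sites for years, so it is left as an option for the Sponsor.
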